SS will be randomized to one of 3 conditions for a 5-week period: (1) VAR plus a mobile CM intervention, (2) VAR plus a non-contingent reinforcement (NR) control condition, and (3) PLA plus the NR condition. During the first week, participants will undergo a standard 7-day medication (VAR or PLA) dose run-up period and will receive voucher-based reinforcement for texting videos of themselves providing CO samples twice per day, regardless of CO level. In Weeks 2-5, participants will continue to text video samples twice per day and will receive voucher reinforcement that is either contingent upon abstinence, or contingent only upon submitting the video (NR). Participants will visit the laboratory each week to complete assessments of smoking, craving, withdrawal symptoms, mood, subjective effects of smoking and psychiatric symptoms. They will also complete the CPT, cognitive battery, measures of quit interest, and provide a saliva sample for cotinine analysis at the beginning and end of the intervention period. At the end of the intervention, participants will be provided with brief advice to quit smoking and will be offered referrals to community treatments. They will also be administered a debriefing questionnaire in which they are asked to guess their medication condition and asked about the intervention acceptability, their willingness to participate in longer CM trials, and their willingness to receive prize-based incentives rather than vouchers.

Two weeks after Session 6, participants will be contacted by phone and asked about the frequency and quantity of cigarette and other nicotine/tobacco product use since the end of the active treatment period. Those indicating that they have been abstinent in the last 7 days will be provided with taxi transportation and compensation to provide CO verification of abstinence. Participants will be asked whether they have contacted and attended any community cessation treatments, and about their current interest in treatment. Participants will again be offered referrals to cessation treatments in the community. This assessment, including CO verification of abstinence, will be repeated 2 weeks later.

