All data will be collected for research purposes only. All forms will be marked with only subject ID, session number and date. All records will be stored in locked files (physical or on computer) in locked rooms accessible only to research staff. Data gathered from people who attend the screening but do not meet inclusion criteria or decide not to participate will be stripped of personal identifiers or links and only the reason for study exclusion will be kept.

Personal information (participant name, address, telephone number, email address, locator contact information) must be collected so that the research assistant can contact people to schedule assessments, call with session reminders and arrange transportation to sessions. These data will be stored in a locked file that does not contain ID code numbers. All other data will be stored in files locked in a separate location with only code numbers identifying subjects and no personal identifiers. A cross-index of code numbers and participant names will be kept in a separate, password-protected computer file that is available only to research staff, PI, and mandated agencies during audits (e.g., study sponsor and Brown University IRB).

Saliva specimens for cotinine analysis will be marked with a study ID number, stored in the locked laboratory suite, and sent to a commercial laboratory for analysis. We will track samples sent and analysis results received using a form stored on a password-protected computer.

Data Analysis Plan

R21 phase

Variables will be examined for distributional assumptions associated with analyses to be used and transformed if necessary. Groups will be compared on demographic and other individual difference measures using t-tests for continuous measures and chi-square tests for categorical measures. Analyses of the effects of Group (VAR, PLA) and Time (Sessions 2-8) on QSU and MNWS-negative affect scores will be conducted using generalized estimating equation (GEE) models (Zeger et al., 1988), which allow for varying numbers of observations per participant (to minimize bias due to attrition) while controlling for autocorrelation (AR1 structure). GEE will also be used to analyze the effects of Group and Time (Screening, Sessions 2 and 8) on BPRS and other psychiatric symptom scores. Mixed 2 x 2 Analysis of Variance tests (ANOVAs) will be used to examine effects of Group and Abstinence (Sessions 1 and 8) on CEQ scale scores,

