Following intent-to-treat principles, all randomized participants will be included in analyses. Baseline characteristics of the groups will be compared using ANOVAs for continuous variables and chi-square tests for categorical variables. CO levels from participants' videos will be averaged to provide a single CO measure for each week. Effects of the treatment groups on dependent measures (CO, total and consecutive abstinent CO samples, cigarettes per day, cotinine, QSU, MNWS, mood, CEQ, Stage of Change, Contemplation Ladder, cognitive scores (baseline co-varied), BPRS, Calgary Scale, AIMS, Simpson-Angus and BARS scores), will be analyzed with generalized linear mixed models (GLMMs) with Group (VAR + CM, VAR + NR, PLA + NR) as the between-subjects factor and Session as the within-subjects factor. We will examine main effects and the Group x Session interaction. This approach controls for correlations from repeated measurements and for person-level covariates. Baseline data will be imputed for missing. Differences will be considered significant when $p \leq .05$ and effect sizes will be calculated (Cohen, 1988). We will examine whether gender and FTND score (≤ 5 vs. ≥ 6) moderate treatment effects by adding these factors (separately) to each model. To examine whether reductions in smoking are mediated by changes in proposed targets, once the Group x Session GLMMs have been conducted, we will add concurrent QSU, MNWS and CEQ Reward and Satisfaction scores as covariates in these models to see the extent to which

smoking outcomes are attenuated by the mediators. We will use the same procedure to explore whether cognitive performance mediates smoking outcomes.

Feasibility outcomes include: median number of sessions attended, percentage of video samples submitted and percentage of those who indicate that they would be willing to participate in a longer CM trial. Responses to open-ended questions on the debriefing questionnaire will be described. Number and type of serious adverse events are expected to be rare so will be reported descriptively. Adverse event ratings will be analyzed individually using one maximum value over the 5 weeks for each person for each expected effect, including the baseline value of each item.

Quality Assurance

Procedures in place to ensure the validity and integrity of the data

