- 6) Changes in Psychiatric Symptoms Secondary to Changes in Smoking Behavior. Changes in smoking can affect how well some psychiatric medications work due to changes in CYP1A2 enzyme activity. We believe the risks of these events are low given the low incidence of such changes in clinical trials, including a trial that included over 4000 smokers with psychiatric disorders (Anthenelli et al., 2016; Evins et al., 2014). However, we will inform participants about these risks and ask participants to provide us with written permission to notify their treating clinician that they are in a study in which they may receive VAR and a behavioral treatment (R33 phase only) that may affect their smoking rate. Adverse events will be collected weekly using a checklist and open-ended questions. In addition, psychiatric symptoms will be assessed with the BPRS and Calgary Scale at every in-person session and movement disorders will be assessed with the AIMS, Simpson-Angus Scale and BARS at the screening and last session. Moderate-to-severe increases in symptoms (e.g., change from mild/moderate category to severe) will trigger review by [name] or [name], who will meet with the participant if needed. Serious adverse events and unexpected related adverse events will be reported to the Brown University IRB as noted above (see **Regulatory Issues** section). Participants will be given contact information so that they can reach the PI, [name], [name], or study staff at any time to report adverse events. Participants reporting suicidal intention at any time (score ≥ 4 on the Columbia Suicide Severity Rating Scale, suicide plan endorsed on the Calgary Depression Scale for Schizophrenia, or spontaneous reports) will be put in contact with [name] or [name] immediately. The clinician will speak with the participant in person if suicidality is reported during a study visit or by phone if it is reported by phone. The clinicians will then determine the next steps to be taken. Having 2 clinicians on this study increases the likelihood that at least one will be available. However, if neither is available, other qualified clinicians at our research center will speak with the participant. The PI will follow any steps recommended by the clinician (i.e., to continue or discontinue participation).

Potential benefits of participation

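### The unrestricted R33 rule that fills missing data with baseline values reaches the psychiatric and movement scales and pulls them, slightly, toward no harm; the matching rule for unsent CO videos needs stating.

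*Combined protocol and SAP*

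**What the plan says.** **R33 missing data.** The Data Analysis Plan, R33 phase, includes all randomized participants. It names the outcomes for the generalized linear mixed models (GLMMs) in one list: CO, total and consecutive abstinent samples, cigarettes per day and cotinine, and also BPRS, Calgary, AIMS, Simpson-Angus and BARS. A few sentences later comes the only missing-data rule: "Baseline data will be imputed for missing". It names no outcome, no reason for missingness and no level (sample, week or visit).

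**Withdrawal and schedule.** Collection and reporting of AEs and SAEs requires withdrawal after a suicide attempt or psychiatric hospitalization. Item 6 of the risks section schedules BPRS and Calgary at every in-person session, while "movement disorders will be assessed with the AIMS, Simpson-Angus Scale and BARS at the screening and last session".

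**R21.** The R21 plan analyses QSU and MNWS negative affect by GEE models, "which allow for varying numbers of observations per participant (to minimize bias due to attrition"), and uses GEE again "on BPRS and other psychiatric symptom scores". It states no imputation, and no analysis of the movement scales.

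**CO videos.** In R33, CO levels from "videos will be averaged to provide a single CO measure for each week". In Week 1 every arm is reinforced for sending samples "twice per day, regardless of CO level". In Weeks 2-5 participants "will receive voucher reinforcement that is either contingent upon abstinence, or contingent only upon submitting the video (NR").

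**Elsewhere.** The DSMB's monitoring activities include settling how missing visits and data are dealt with, but no rule is given.

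**The concern.** For a smoking outcome, filling in baseline assumes no benefit after drop-out, which is a familiar cautious choice. On a scale that is there to show worsening, the same rule assumes no harm. Here the missingness can be caused by the worsening, because psychiatric hospitalization and suicide attempt both force withdrawal. The movement scales have a single follow-up point, so a filled value can be a participant's only follow-up value.

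What is at stake is the between-arm comparison on these scales in a population for which the plan itself promises monitoring of psychiatric symptoms. The planned GLMM can use unequal numbers of observations, so the filling is not needed to keep withdrawn participants in the analysis.

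The same sentence leaves the CO outcome open. It does not say whether baseline replaces each unsent video before weekly averaging or only a week with no video, or whether an unsent video ends a run of consecutive abstinent samples. CO is a named smoking measure in R33 Aim 1, and the sample size section says R33 will rest on feasibility and effect sizes.

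**Working it through.** The plan gives no figure on this point to reproduce. It also gives no post-randomization missing rate, no BPRS standard deviation, no video submission rate and no mean baseline CO. Everything below marked as assumed is illustration.

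**Arm size.** The plan has 60 enrolled (20 per group) and 20% attrition before randomization: 20 × 0.80 = 16 per arm, or 48 in total, as stated.

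**1. BPRS, one withdrawal among 16.** Assumed: a 10-point rise measured at Session 3, then withdrawal, so Sessions 4-6 are missing; the other 15 do not change; SD 8. The quantity is the arm's mean change averaged over Sessions 2-6.

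| What happens after Session 3 | True value | Baseline rule |
|---|---|---|
| Rise persists | (4 × 10)/5/16 = 0.50 | 10/5/16 = 0.125 |
| Fades evenly (10, 6.67, 3.33, 0) | 20/5/16 = 0.25 | 0.125 |
| Resolves at once | 10/5/16 = 0.125 | 0.125 |

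The observed-score model was computed by generalized least squares on Sessions 1-6 with free session means. The Session 3 mean rises by 10/16 = 0.625, and the missing sessions borrow from it through the correlation:

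- AR1, correlation r: 0.625 × (1 + r + r² + r³)/5 = 0.272 (r = 0.6) or 0.369 (r = 0.8).
- Compound symmetry: each later session gets 0.625 × r/(1 + 2r), which is 0.170 (r = 0.6) or 0.192 (r = 0.8). The average (0.625 + 3 × that value)/5 is 0.227 or 0.240.

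Difference from the baseline rule: 0.227 − 0.125 = 0.10 up to 0.369 − 0.125 = 0.24 points. Divided by 8, that is about 0.01 to 0.03 SD.

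- If the rise persists, the baseline rule is 0.375 too low and the observed-score model 0.13 to 0.27 too low.
- If it resolves at once, the baseline rule is exact and the observed-score model is 0.10 to 0.24 too high.
- If the rise was never measured, both give about 0.

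**2. Movement scales.** If k of 16 lack a last-session score for unrelated reasons, filling no change multiplies the arm's mean change by (16 − k)/16. The shrinkage is 1/16 = 6%, 2/16 = 12.5% and 4/16 = 25% for k = 1, 2 and 4 (assumed counts). An observed-score model does not shrink it. If the score is missing because of worsening, neither method recovers it.

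**3. Weekly CO.** Assumed: no true arm difference; half of the 14 weekly samples follow smoking; abstinent CO 3 ppm; baseline CO 20 ppm; the contingent arm sends 90% of abstinent and 40% of smoking samples; each non-contingent arm sends 85% of all samples.

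- Sent-only mean = Σ(share × sent × CO)/Σ(share × sent).
- Per-video filled mean = Σ share × (sent × CO + unsent × 20).

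| Smoking CO | Sent-only, contingent v non-contingent | Error | Per-video filled | Error |
|---|---|---|---|---|
| 20 | 8.23 v 11.50 | −3.3 | 12.35 v 12.78 | −0.4 |
| 16 | 7.00 v 9.50 | −2.5 | 11.55 v 11.08 | +0.5 |
| 11 | 5.46 v 7.00 | −1.5 | 10.55 v 8.95 | +1.6 |

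If 60% or 20% of smoking samples are sent instead of 40%, the sent-only error at smoking CO 16 runs from −1.3 to −4.1 and the filled error from +0.1 to +0.9. The unstated choice can therefore change the size of the CO contrast and sometimes its sign. Under the 40% rate the contingent arm would submit 0.5 × 0.9 + 0.5 × 0.4 = 65% of videos, against 85%.

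**The case against.** **The sentence may not mean this.** It is short, does not mention withdrawal, and could mean that missing baseline values are imputed. That stands as a caution: the reach to withdrawn participants is inferred from the analysis plan, the withdrawal criteria and the assessment schedule together. On the other reading the bias disappears. A reader might then infer that R33 has no means of handling missing follow-up, but that goes too far, since a GLMM can be fitted to unequal numbers of observations.

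**The effect is tiny and harm is caught elsewhere.** Both are largely true. Moderate-to-severe symptom increases trigger clinician review. SAEs are reported by number and type. "Adverse event ratings will be analyzed individually using one maximum value over the 5 weeks for each person", and the DSMB reviews drop-outs and their reasons. A reader might infer that the rule would hide a safety signal; the documents do not support that. What stands is a bias in a known direction on the scale comparisons, which a model already in the plan reduces when the worsening lasts.

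**R21 and R33 may differ.** They may, and the difference is not a contradiction. The attrition rationale is attached to QSU and MNWS, with psychiatric scores following by the same method. The contrast covers psychiatric scores only and does not extend to the movement scales. It shows only that an analysis of available observations was acceptable for the same type of score.

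**The CO point is a missing detail.** Mostly so. An unsent video already adds nothing to a simple total of abstinent samples, so the open items are the weekly mean and the consecutive runs. A reader might infer that contingent-arm participants will withhold smoking samples. No section reports this; it is an inference from how payment is arranged.

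**Conclusion.** The point holds in limited form. Taken at its natural reading, the R33 rule scores participants withdrawn for psychiatric reasons as unchanged at later sessions and turns a missing last-session movement score into no change. It therefore biases these scales toward no harm whenever worsening lasts beyond withdrawal.

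The expected size is small: about 0.01 to 0.03 SD between methods on BPRS for one withdrawal in 16, and a proportional shrinkage of k/16 on the movement scales. Both depend on assumed inputs. If the worsening resolves at once, the baseline rule is the more accurate of the two. The change is worth making because it is cheap and the direction of the bias is the wrong one for a safety scale, not because the distortion is large.

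The CO question is secondary. The plan needs a stated rule, and the illustration shows why it should be fixed before the arms are known. It does not show that the planned CO result is biased.

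**What to change.** **Scales.**
- Restrict baseline imputation to the smoking measures.
- Fit the planned GLMM to all observed psychiatric and movement scores without imputation.
- Report by arm the number of psychiatric withdrawals and of missing last-session scores.
- Add a sensitivity analysis that assigns worse-than-baseline scores after such a withdrawal.

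**CO, before R33 is unblinded.**
- In the analysis counts, treat an unsent video as non-abstinent and as breaking a consecutive run.
- Name one primary rule for weekly CO, including what is done in a week with no videos, and keep the other as a sensitivity analysis. Present neither as unbiased.
- Report the percentage of videos submitted by arm for Week 1, when payment does not depend on CO in any arm, and for Weeks 2-5. A fall in the contingent arm alone would be consistent with selective sending. Cigarettes per day and cotinine, which do not depend on videos, serve as a check.

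**Cost.** SAP wording and minor programming, with no new data; percentage submitted is already a planned outcome. An observed-score model does not fully correct informative withdrawal, and in the BPRS example it overstates by 0.10 to 0.24 points if the rise resolves at once. Counting unsent videos as non-abstinent is harsh when a video fails for technical reasons. The two CO versions may disagree, or may err in the same direction (−3.3 and −0.4 at smoking CO 20), so the CO effect could remain inconclusive.

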Analyses will examine the effects of VAR versus PLA on time to relapse and on smoking urges and negative affect during abstinence (primary targets), smoking satisfaction and reward during Session 8 (secondary targets), and cognitive performance (exploratory target). We will also examine the extent to which the effects of VAR on time to relapse are mediated through its effects on these mechanisms. If VAR reduces either the primary or secondary targets by $\geq 20\%$ in $\geq 50\%$ of the sample (go/no-go rule), this research will proceed to an R33 phase.

Aims of the R33 Phase

Aim 1: To compare the effects of VAR + mCM, VAR + non-contingent reinforcement (NR) and PLA + NR on smoking measures (CO levels, cigarettes per day) and target mechanisms (smoking urges and negative affect during abstinence, reinforcing effects of a smoking lapse, cognitive function) in SS over a 5-week period.

Aim 2: To examine the extent to which the effects of the treatments on the smoking measures are mediated through the effects of the treatments on the target mechanisms.

Aim 3: To assess the feasibility and acceptability of a multi-week VAR + mCM intervention in SS.

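### R33 Aim 2 reads attenuation by same-week target scores as mediation, but a same-week score cannot separate target-to-smoking from smoking-to-target

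*Combined protocol and SAP*

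**What the plan says.** R33 Aim 2 (Aims of the R33 Phase) asks how far the "effects of the treatments on the smoking measures are mediated through the effects of the treatments on the target mechanisms". The method is in the Data Analysis Plan, R33 phase. After the Group x Session GLMMs, "we will add concurrent QSU, MNWS and CEQ Reward and Satisfaction scores as covariates in these models", to see how far "smoking outcomes are attenuated by the mediators". For R33 the plan gives no lag, no adjustment for earlier smoking, no separate paths and no interval for an indirect effect.

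On timing, the same section says "CO levels from participants' videos will be averaged to provide a single CO measure for each week". The R33 design description has one laboratory visit per week, at which craving, withdrawal, subjective effects of smoking and smoking itself are all assessed. The treatment period is 5 weeks, and follow-up is anchored as "Two weeks after Session 6, participants will be contacted by phone".

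For cognition: "We will use the same procedure to explore whether cognitive performance mediates smoking outcomes". In R33 the cognitive battery is given only twice, in the same sentence that has participants "provide a saliva sample for cotinine analysis at the beginning and end of the intervention period".

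**The concern.** Mediation needs the target to act on smoking. The plan pairs a week's smoking with a target score from that same week, so the model is equally consistent with smoking acting on the target.

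The trial's own material makes the reverse path likely. The R21 phase manipulates abstinence and analyses its effect on the CEQ scales. The nicotine withdrawal entry under Potential risks of participation lists craving, irritability, anxiety and low mood as consequences of abstaining. In R33 the contingent vouchers pay for abstinence directly, so in the VAR + CM arm smoking can change first and the scores follow.

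At stake is what the phase can say about mechanism. The planned summary, an extent of attenuation, could be positive when no target has any effect on smoking.

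**Working it through.** **No stated figure to reproduce.** The documents give no effect size, power or correlation for R33 mediation. The check is therefore one of time order, followed by the size of the artefact under stated assumptions.

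**Time order.** Five treatment weeks and a final Session 6, with the later call asking about use since active treatment ended, fit Session 1 as baseline and Sessions 2–6 closing Weeks 1–5. On that mapping the score follows the CO readings it is paired with. This is an inference.

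**Contrast with R21.** There the Session 8 scores are set against latency counted from the start of Session 8, so the score opens the outcome window. R21 also specifies the a, b, c and c' paths, with bootstrap intervals if the product is not normally distributed. R33 has neither the ordering nor the interval.

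**Closed form with zero true mediation.** Let Y be smoking, T treatment and M the score:

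- Y = τT + e, with Var(e) = σ²
- M = λY + d, with Var(d) = ω², and no path from M to Y

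Within arm, the slope of Y on M is β = λσ² / (λ²σ² + ω²). Treatment shifts M by λτ. The coefficient of T after adding M is therefore

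τ − βλτ = τ(1 − ρ²), where ρ² = λ²σ² / (λ²σ² + ω²).

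Apparent attenuation is ρ²: 0.3² = 9%, 0.5² = 25%, 0.7² = 49%. The sign of λ drops out. Attenuation appears whether smoking raises or lowers the score, so it does not even show that lower craving goes with lower smoking.

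**Repeated measures.** The closed form ignores stable differences between people. A random-intercept simulation used two arms of 16 (48 randomized over three arms, if equal), Weeks 2–5, 600 runs per setting, a treatment effect of 1 SD and true mediation zero. The effect size, the correlations and the between-person shares of smoking variance are assumptions.

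| Within-arm correlation | Share 0 | Share 0.3 | Share 0.6 |
|---|---|---|---|
| .3 | 9% | 7–8% | 5% |
| .5 | 25% | 22% | 15% |
| .7 | 49% | 46% | 35% |

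A hand check at correlation .5 and share 0.6, with λ = 1 and σ² = 1: ω² = (1 − 0.25)/0.25 = 3. The within-person slope is 0.4/(0.4 + 3) = 0.12. The slope for four-week means is (0.6 + 0.4/4)/(0.6 + 0.4/4 + 3/4) = 0.70/1.45 = 0.48. The mixed model blends the two, and the simulated 15% lies between them. So ρ² is the upper end of the range.

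**With the preceding session's score instead.** In the same simulation apparent attenuation fell to between −1% and 2%. The lagged score was significant in about 5–13% of runs, somewhat above nominal because smoking is correlated within person. With preceding-week CO also in the model, a separate simulation (AR(1) of .6 in CO, 800 runs per setting) gave about 5–7%. That is the reason to adjust for earlier smoking.

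**The case against.** Four objections have force.

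1. **Visit timing.** A reader might infer that the scores demonstrably come after the smoking. The documents do not print visit days or map sessions to CO weeks, so that cannot be stated as fact. What stands is weaker and sufficient: nothing in the plan places the score first.

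2. **Covariate significance.** With zero mediation, the concurrent score was significant in 70–95% of simulated trials at correlation .3 and 99–100% at .5 or more. A reader might call this a false-positive rate for the planned analysis. It is not. The plan judges the extent of attenuation, not the covariate's p-value, and in those simulations score and smoking truly are correlated.

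3. **Consequence.** A reader might infer that the decision on a larger trial hangs on this result. Power Calculation and Sample Size, R33 phase, bases it on feasibility and effect sizes and says the phase is not powered for group differences. Only the mechanism claim is affected. Pilot status excuses imprecision, but this bias would not shrink with more participants.

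4. **The lag has its own bias.** If mediation acts entirely within the week, a lagged score largely misses it. Simulating that case, the lagged product recovered 37–42% of the total effect under one set of assumptions and essentially none under another. On the inferred mapping, the score opening Week 2 also precedes any contingent voucher, so the first effect of CM cannot pass through it. Preceding-week smoking is post-randomisation and already carries treatment effect, so conditioning on it changes the estimand. This rules out simply replacing one model with the other.

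On cognition, a reader might infer that the only on-treatment score follows every smoking outcome. It does not: cotinine is taken at the same two points, and smoking is asked about again at the two follow-up calls. The plan also calls this analysis exploratory. But a measure taken only at the beginning and end cannot go through a week-by-week procedure.

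**Conclusion.** The concern holds in this form: the R33 mediation analysis does not identify direction. If targets only respond to smoking, it would still report attenuation of roughly 5–9% at a within-arm correlation of .3 and 15–25% at .5. The spread reflects between-person shares of variance from 0.6 down to 0. These figures assume zero true mediation and correlations that the documents do not supply. They show what the method can produce by itself and do not predict the trial's result.

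It does not follow that all observed attenuation would be reverse causation. Some may be real mediation, and the plan cannot say how much. The wording should be changed before the R33 data are analysed. The Group comparisons on smoking are unaffected.

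**What to change.** In the Data Analysis Plan, R33 phase:

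- State which session's scores are paired with which week's CO mean.
- Keep the concurrent model, but state that it shows association only and that its attenuation is not evidence of direction.
- Add a time-ordered model: QSU, MNWS and CEQ Reward and Satisfaction from the preceding session predict the following week's CO and cigarettes per day, adjusted for preceding-week smoking.
- For each group contrast, report the product of Group-to-target and target-to-next-week-smoking with a bootstrap interval, resampling participants. This brings R33 close to the R21 approach.
- Claim mediation only where the time-ordered model supports it.
- Report cognition as association only.

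The change is to wording and analysis; the weekly visits and videos already supply the data. The price should be stated in the plan. The lagged model can miss same-week mediation, it has no earlier on-drug score for Week 1, the score opening Week 2 comes before contingent vouchers, and the prior-smoking adjustment conditions on a post-randomisation variable. Its estimate should be presented as conservative and read beside the concurrent one. With 48 participants, the interval should be expected to be wide.
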